1.2 BACKGROUND ON GDC-6599

GDC-6599 is a small molecule inhibitor of the TRPA1 channel that is under development as a potential oral therapy for the treatment of patients with CRC with asthma or UCC.

[REDACTED]

GDC-6599, administered orally (PO), was well tolerated in both rats and cynomolgus monkeys at doses up to 50 mg/kg/day for 4 weeks. The most significant GDC-6599-related finding was a dose-dependent, reversible prolongation of the coagulation parameters aPTT and PT in both rats and monkeys.

[REDACTED]

GDC-6599 *has been investigated in a completed Phase Ia/b single ascending dose (SAD) and multiple ascending dose (MAD) study (GA43010) in approximately 81 healthy volunteers to explore safety, and the pharmacokinetic and pharmacodynamic profile of the agent. Pharmacodynamic target (TRPA1) inhibition *has been evaluated* using the AITC dermal challenge model (Joseph et al. 2021). No significant clinical, laboratory, or ECG findings have been observed in the initial six dosing cohorts of the SAD portion and three cohorts of the MAD portion of Study GA43010. Based upon the available clinical data, the clinical dose for the current Phase IIa protocol (GA43590) is [REDACTED] (█; see Section 3.3.2). No prior clinical experience with GDC-6599 exists in patients.*

Refer to the GDC-6599 Investigator's Brochure for details on nonclinical and clinical studies.

1.3 STUDY RATIONALE AND BENEFIT–RISK ASSESSMENT

This Phase IIa cough profiling study will be conducted to evaluate potential inhibition of cough by GDC-6599, a small molecule inhibitor of TRPA1, and its effects on mannitol-induced cough and airway hypersensitivity in a subset of patients with CRC with asthma or UCC. The effects of GDC-6599 on cough and airway inflammation will also be assessed in a subgroup of patients with CRC who have a history of COPD.

The rationale for targeting TRPA1 for the treatment of chronic cough, asthma, and COPD is driven by the potential role of TRPA1 in contributing to airway smooth muscle contraction, sensory hypersensitivity, and neurogenic inflammation, which may lead to bronchoconstriction, AHR, and symptoms such as cough. Anticipated beneficial effects of targeting TRPA1 with GDC-6599 include reduction in bronchoconstriction and cough hypersensitivity in asthma and COPD and a reduction of cough hypersensitivity-associated CRC with asthma or UCC.

GDC-6599 *has been tested* in healthy volunteers in a completed Phase Ia/b SAD/MAD Study GA43010. No prior clinical experience with GDC-6599 exists in patients. The rationale for conducting the current study in patients with chronic cough is to evaluate the efficacy, safety, pharmacokinetics, and organ-specific pharmacodynamics (target inhibition in lung) in a relevant patient population.

An assessment has been conducted to determine whether the coronavirus disease 2019 (COVID-19) pandemic has any impact on the benefit-risk assessment of this study including, but not limited to, the patient population under study and study treatment. Review of the summary safety data generated in the initial *six dosing cohorts* of the SAD portion and three cohorts of the MAD portion of the Phase Ia/b SAD/MAD study GA43010 of the potent TRPA1-inhibitor GDC-6599 suggests that inhibition of the TRPA1 receptor is not associated with a higher frequency of infections or clinically significant findings in hematology parameters. Combined with further review of the toxicology data and the mechanism of action of GDC-6599, no impact is anticipated. The safety monitoring and management guidelines and risk mitigation measures provided in the study are considered adequate.

2. OBJECTIVES AND ENDPOINTS

This Phase IIa, multicenter, randomized, double-blind, placebo-controlled, crossover study will evaluate the efficacy, safety, pharmacokinetics, and pharmacodynamic (PD) effects of GDC-6599 compared with placebo in patients with a history of chronic cough. It will assess the potential benefit of GDC-6599 to reduce cough frequency and severity in patients with a diagnosis of CRC with asthma, UCC, or CRC with COPD. The study will also *explore the effects* of GDC-6599 on mannitol-induced cough and/or AHR and the value of mannitol-induced cough hypersensitivity and/or AHR as a prognostic tool in patients with CRC with asthma, UCC, or CRC with COPD as a measure of TRPA1 airway activity. Specific objectives and corresponding endpoints for the study are outlined in [Table 1](#) below.

Table 1 Objectives and Corresponding Endpoints

Primary Objective	Corresponding Endpoint
• To evaluate the efficacy of GDC-6599, as compared with placebo, in patients with CRC with asthma or UCC	• Change in cough frequency per hour, assessed objectively over 24 hours (24-hour OCC) using VitaloJAK® cough recorder, from baseline to Day 14
Secondary Objective	Corresponding Endpoints
• To evaluate the efficacy of GDC-6599, as compared with placebo, in patients with CRC with asthma or UCC	• Change in the severity of cough, as assessed through the use of the patient-reported cough severity VAS and NRS scores, from baseline to Day 14
Safety Objective	Corresponding Endpoints
• To evaluate the safety of GDC-6599 compared with placebo	• Incidence and severity of adverse events, with severity determined according to the DAIDS toxicity grading scale ^a • Change from baseline in targeted vital signs • Change from baseline in targeted clinical laboratory test results
Pharmacokinetic Objective	Corresponding Endpoints
• To characterize the PK profile of GDC-6599	• Plasma concentration of GDC-6599 at specified timepoints
Exploratory Objectives	Corresponding Endpoints
• To evaluate mannitol-induced cough response as a measure of TRPA1 airway activity and treatment benefit of GDC-6599, as compared with placebo, in patients with CRC with asthma or UCC	• Change in cough hypersensitivity to mannitol, measured as the CDR to mannitol, from baseline to Day 14

24-hour OCC=objective cough count over 24 hours; AHR=airway hyperresponsiveness, expressed as RDR (calculated as maximum percent decrease in FEV₁ [relative to baseline of mannitol challenge] after the last dose of mannitol divided by cumulative dose of mannitol, and PD15 (defined as provoking dose of mannitol that induces a 15% decrease in FEV₁); CDR=coughs-per-dose ratio, calculated as total number of provoked coughs divided by cumulative dose of mannitol and expressed as coughs per 100 mg of mannitol; CRC=chronic refractory cough; DAIDS=Division of AIDS; FEV₁=forced expiratory volume in 1 second; NRS=Numeric Response Scale; PK=pharmacokinetic; RDR=response-dose ratio; UCC=unexplained chronic cough; TRP=transient receptor potential; TRPA1=TRP ankyrin 1; VAS=visual analog scale.

^a Adverse events will be graded according to the DAIDS Table for Grading the Severity of Adult and Pediatric Adverse Events (HSS 2017), with slight modifications for clarity and for alignment with internal practices (see Section 5.3.3 and [Appendix 10](#)).

Table 1 Objectives and Corresponding Endpoints (cont.)

Exploratory Objectives (cont.)	Corresponding Endpoints (cont.)

 To evaluate mannitol-induced airway smooth muscle hyper-responsiveness as a measure of TRPA1 airway activity and treatment benefit of GDC-6599, compared with placebo, in patients with CRC with asthma or UCC 	
 Change in mannitol-induced AHR from baseline to Day 14

 To evaluate the efficacy of GDC-6599, as compared with placebo, across each chronic cough disease subgroup 	
 Change in 24-hour OCC collected using the VitaloJAK cough recorder from baseline to Day 14 [REDACTED] Change in FEV_1 from baseline to Day 14 [REDACTED] Change in the severity of cough, as assessed through the use of the patient-reported cough severity VAS score, from baseline to Day 14 Change in the severity of cough, as assessed through the use of the patient-reported cough severity NRS score, from baseline to Day 14 [REDACTED]

 To evaluate cough hypersensitivity and AHR to mannitol across chronic cough disease subgroups 	
 CDR to mannitol across patients with different background diseases AHR to mannitol across patients with different background diseases

 [REDACTED] 	
 [REDACTED] [REDACTED]

24-hour OCC=objective cough count over 24 hours; AHR=airway hyperresponsiveness, expressed as RDR (calculated as maximum percent decrease in FEV_1 [relative to baseline of mannitol challenge] after the last dose of mannitol divided by cumulative dose of mannitol, and PD15 (defined as provoking dose of mannitol that induces a 15% decrease in FEV_1); CDR=coughs-per-dose ratio, calculated as total number of provoked coughs divided by cumulative dose of mannitol and expressed as coughs per 100 mg of mannitol; COPD=chronic obstructive pulmonary disease; CRC= chronic refractory cough; FEV_1 =forced expiratory volume in 1 second;

[REDACTED]; [REDACTED] NRS = Numeric Response Scale; RDR = response-dose ratio; TRP = transient receptor potential; TRPA1 = TRP ankyrin 1; UCC = unexplained chronic cough; VAS = visual analog scale.

Table 1 Objectives and Corresponding Endpoints (cont.)

Exploratory Objectives (cont.)	Corresponding Endpoints (cont.)
• [REDACTED]	• [REDACTED] • [REDACTED] • [REDACTED] • [REDACTED] • [REDACTED]
• [REDACTED]	• [REDACTED]
• To identify and/or evaluate biomarkers that are predictive of response to GDC-6599 (i.e., predictive biomarkers), are early surrogates of efficacy of GDC-6599 treatment, and can provide evidence of GDC-6599 activity (i.e., PD biomarkers, pathway inhibition) as compared with placebo,	• Levels of biomarkers [REDACTED] at baseline and Day 1 through Day 14
• To evaluate potential relationships between drug exposure and the activity, efficacy, and safety of GDC-6599	• Plasma concentration and PK parameters • PD biomarker endpoints • Efficacy/activity endpoints • Safety endpoints

24-hour OCC=objective cough count over 24 hours; AHR=airway hyperresponsiveness, expressed as RDR (calculated as maximum percent decrease in FEV₁ [relative to baseline of mannitol challenge] after the last dose of mannitol divided by cumulative dose of mannitol, and PD15 (defined as provoking dose of mannitol that induces a 15% decrease in FEV₁); CDR=coughs-per-dose ratio, calculated as total number of provoked coughs divided by cumulative dose of mannitol and expressed as coughs per 100 mg of mannitol; COPD=chronic obstructive pulmonary disease; CRC= chronic refractory cough; FEV₁=forced expiratory volume in 1 second; [REDACTED]
PD=pharmacodynamic; PK=pharmacokinetic; RDR=response-dose ratio; UCC=unexplained chronic cough; VAS=visual analog scale.

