- In Section 2 (Table 1) and Section 4.5.5, to clarify the exploratory endpoint of change in mannitol-induced airway hyperresponsiveness (AHR), AHR has been defined as follows: AHR is expressed as response-dose ratio (calculated as maximum percent decrease in FEV₁ [relative to baseline of mannitol challenge] after the last dose of mannitol divided by cumulative dose of mannitol, and PD15 (defined as provoking dose of mannitol that induces a 15% decrease in FEV₁). In this table, change in FEV₁ from baseline to Day 14 has been added as an exploratory endpoint to better evaluate the efficacy of GDC-6599, as compared with placebo, across each chronic cough disease subgroup. To support the new exploratory endpoint, the timing of spirometry has been clarified and an assessment of pre-bronchodilator spirometry has been added on Day 29 (Appendix 1, footnote s).

- In Section 3.1, Appendix 1, and [REDACTED] the washout periods in the schedule of activities have been updated to a minimum of 14 days (Days 15–28) to allow for cough and inflammation to return to baseline prior to initiating the second treatment period, including the 24-hr objective cough count—assessment at the pretreatment visit (Day 29), to provide a baseline prior to initiating treatment on Day 30. This change aligns with the original intent of the protocol. Subsequent timepoints have been adjusted accordingly.
- In Sections 3.1.1 and 4.5.5 and in Appendix 1 mention of the recording of acute coughs induced during the mannitol challenge using the VitaloJAK system has been removed as manual cough counts during the mannitol challenge cannot be validated in this manner. Details on cough counting during the mannitol challenge are provided in the mannitol challenge test guidance document.
- In Sections 3.1.2 and 6.8, clarification has been provided regarding the structure, roles, and responsibilities of the Internal Monitoring Committee.
- In Figure 1 the coughs-per-dose ratio (CDR) inclusion criterion in the Study Schema has been amended for consistency with the CDR-related inclusion criterion in Section 4.1.1.
- In Sections 4.1.1 and 4.1.2, eligibility criteria have been amended to better define the patient population and reflect the underlying patient population that may eventually benefit from the investigational drug as follows:

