3.3.6 Rationale for 24-Hour Cough Monitoring and Continuous Digital Cough Assessment

Cough will be assessed by the VitaloJAK semi-automated cough counting system. VitaloJAK is the only clinically validated, 510K-cleared, and Conformité Européenne-marked medical device system for the objective measurement of cough (Birring et al. 2008; Barton et al. 2012; Smith et al. 2021). VitaloJAK has been used to measure cough frequency as either a primary or secondary endpoint in several Phase II and III programs, including gefapixent, BAY1817080, and BLU-5937, targeting patients with UCC or CRC. The treatment effect in this study will be analyzed on the basis of cough frequency data (24-hour OCC) collected via VitaloJAK.

While VitaloJAK is the current gold standard for measuring cough frequency, it is limited to a maximum of 24-hour recordings. Previous placebo-controlled studies suggest there is significant day-to-day variability in 24-hour OCC that reduces the probability of detecting treatment differences based upon a single 24-hour data collection. [REDACTED]

[REDACTED]

[REDACTED]

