4.3.2 Study Treatment Dosage, Administration, and Compliance

The treatment regimens are summarized in Section [3.1](#).

GDC-6599 or placebo will be administered orally at a dose of [REDACTED]. GDC-6599 or placebo tablets should be taken approximately [REDACTED] [REDACTED]. For Visit 2 (Day 1), Visit 4 (Day 14), Visit 5 (Day 30), and Visit 7 (Day 43), [REDACTED] [REDACTED]. Patients may self-administer [REDACTED] [REDACTED] for Visit 3 (Day 7) and Visit 6 (Day 36). Patients will self-administer all other doses of study drug at home.

All active and placebo tablets will be administered by mouth, followed immediately with water. The tablets should be swallowed whole; they should not be chewed, cut, broken, or crushed. Study drug may be taken with or without food. If a dose of study drug is missed (i.e. delayed by more than 4 hours) or if vomiting occurs when the dose is taken, the patient should resume dosing with the next scheduled dose without compensating for the missed dose.

For doses administered in the clinic, compliance will be assessed by a visual check of the mouth and hand performed by site staff. For self-administered doses, patients will be required to record the time they took each dose every day in a study drug compliance electronic diary; missed doses will also be recorded. Patients will be instructed to bring all unused study medication and their study drug compliance diaries to the clinic at specified study visits (see schedule of activities in [Appendix 1](#)). Compliance will be assessed by reviewing diaries and counting returned tablets.

Refer to the pharmacy manual for detailed instructions on drug preparation and administration.

Details on treatment administration (e.g., dose and timing) should be noted on the Study Drug Administration electronic Case Report Form (eCRF). Cases of overdose, medication error, drug abuse, or drug misuse, along with any associated adverse events, should be reported as described in Section 5.3.5.11.

Guidelines for treatment interruption or discontinuation for patients who experience adverse events are provided in Section 5.1.3.1.

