4.5.6 Cough Monitoring

Objective cough counting will be conducted as per the study's pulmonary function and cough monitoring guidance documents, in addition to standard manual methods of counting during the mannitol challenge tests (Koskela et al. 2004; Koskela et al. 2018). Cough numbers will be assessed by the VitaloJAK (Vitalograph Inc.) semi-automated cough-monitoring system. The VitaloJAK device will record ambulatory audio for 24 hours from two channels, a lapel microphone (air) and a chest-facing sensor (skin). A software algorithm will remove non-cough sounds from the 24-hour audio recordings, compressing the files to less than 10% (on average) of the original length enabling manual analysis to be completed more quickly. The recordings will be reviewed by trained Vitalograph analysts who will count individual explosive cough sounds, yielding hourly and 24-hour OCCs.

The VitaloJAK counting device will be provided to all study sites. The VitaloJAK device will be used to record spontaneous coughs during for 24 hours on the first day of screening, for 24 hours prior to the first dose of study drug of each treatment period, and for 24 hours following each optional mannitol challenge test during each treatment period (or for 24 hours beginning approximately 3 hours after study drug administration, if mannitol challenge test is not performed), as outlined in the schedule of assessments ([Appendix 1](#)). The pulmonary function and cough monitoring guidance documents will include information on equipment, procedures, patient instructions, and precautions regarding the use of the VitaloJAK. Cough monitoring will be performed per the study's cough monitoring guidance documents. Required training on equipment use and data transfer methods will be provided.

[REDACTED]

[REDACTED]

[REDACTED]

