6.4 EFFICACY ANALYSES

The purpose of this study is estimation and hypothesis generation regarding efficacy and activity of GDC-6599, as compared with placebo, in patients with CRC with asthma or UCC. The effects of GDC-6599 on cough will also be assessed in a subgroup of patients with CRC with COPD. Statistical summaries will be descriptive in nature (e.g., incidence rates, means, standard deviations, and percentiles). Any patients who received any amount of GDC-6599 or placebo will be included in the analyses. Patients will be grouped according to the treatment received in a given period. Final results will be summarized for GDC-6599 and for the placebo periods. No formal hypothesis testing will be performed.

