Appendix 1: Schedule of Activities for Part A and Part B

- u Post-bronchodilator spirometry replaces the recovery spirometry assessment [*if required*] following mannitol challenge at screening. Post-bronchodilator spirometry should be performed per the pulmonary function and cough monitoring guidance documents at least 1 hour following the mannitol challenge test or on a separate study visit within the screening period before or after the mannitol challenge test.
- v Details on cough monitoring are provided in Section 4.5.6 and in the pulmonary function and cough monitoring guidance documents.
- w Cough monitoring with the VitaloJAK cough recorder will begin on the first day of screening and will continue for 24 hours if the screening visits occur over multiple visits. If screening visit occurs during a single visit, use of the VitaloJAK cough recorder should start at least 30 minutes after the mannitol challenge test.
- x Cough monitoring with the VitaloJAK cough recorder will begin a minimum of 24 hours prior to study drug administration and will conclude on the day of study drug administration.
- y Cough monitoring with the VitaloJAK cough recorder will begin at the *end of the mannitol challenge test* (i.e., immediately after spirometry following the last dose of mannitol or after the final spirometry following the recovery period [*if required*]) and will continue for 24 hours after mannitol challenge recovery period. If the mannitol challenge test is not performed, cough monitoring with the VitaloJAK cough recorder will begin approximately 3 hours after study drug administration.

z [REDACTED]

aa Study drug (GDC-6599 or placebo) will be administered [REDACTED] on Days 1–14 and on Days 30–43. [REDACTED]

bb [REDACTED]

[figure not shown]
cc [REDACTED]

[figure not shown]
dd After informed consent has been obtained but prior to initiation of study drug, only serious adverse events caused by a protocol-mandated intervention should be reported. After initiation of study drug, all adverse events will be reported until 28 days after the final dose of study drug.

[figure not shown]
Reference:

[figure not shown]

[figure not shown]

[figure not shown]

Appendix 6

Visual Analog Scale

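### Section 6.4 plans no baseline adjustment, so a drug–placebo contrast of change scores gives up precision that recordings already in the schedule could recover

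*Combined protocol and SAP*

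**What the plan says.** Table 1 in Section 2 gives the primary endpoint as "Change in cough frequency per hour, assessed objectively over 24 hours (24-hour OCC) using VitaloJAK® cough recorder, from baseline to Day 14". Neither Section 2 nor Section 6 says which recording is the baseline or on what scale the change is taken.

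Section 4.5.6 has the recorder worn "for 24 hours on the first day of screening" and again "for 24 hours prior to the first dose of study drug of each treatment period". Footnote x of Appendix 1 agrees: "Cough monitoring with the VitaloJAK cough recorder will begin a minimum of 24 hours prior to study drug administration". The summary of changes at the front of the protocol describes the recording before Period 2 as an "assessment at the pretreatment visit (Day 29), to provide a baseline prior to initiating treatment on Day 30". Under Section 4.3.2 the end-of-period visits fall on Day 14 and Day 43.

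Section 6.4 describes the aim as estimation and hypothesis generation, plans descriptive statistics and no test, and adds: "Final results will be summarized for GDC-6599 and for the placebo periods". It names no model, paired difference or baseline adjustment. Section 3.3.3 justifies the crossover on the ground that patients act as their own controls. Section 3.3.6 reports from earlier placebo-controlled studies that "there is significant day-to-day variability in 24-hour OCC that reduces the probability of detecting treatment differences based upon a single 24-hour data collection".

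**The concern.** In a two-period crossover, stable differences between patients cancel when the two periods are compared, with no baseline needed. If each period's one-day baseline is then subtracted, the contrast carries four single-day recordings instead of two. Section 3.3.6 itself warns about the noise in single-day recordings. A baseline recording helps only to the extent that it tracks the same period's outcome better than the other period's. Subtraction gives it full weight regardless, whereas using it as a covariate lets the data set the weight.

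What is at stake is the precision of the main estimate. The study is designed to estimate, its cohorts are 20 to 30 patients, and patients who drop out are not replaced. Someone who takes the planned summaries of change by treatment and subtracts one from the other gets the unadjusted contrast.

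**Working it through.** **Inputs from the documents.** Four recordings per patient: pre-dose (B1, B2) and end of period (Y1, Y2), at about Days 0, 14, 29 and 43. Part A has about 60 patients. Section 6.1 gives 20 to 30 per cohort with no effect size, SD or power, so there is no plan figure to reproduce beyond the enrolment sums, which agree (30 + 30 = 60; 60 + 20 = 80).

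**Assumed, because the documents give none.** A common variance s² per recording, a correlation rw between two recordings in the same period, and rb between recordings in different periods.

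**Formulas.** Let DY = Y1 − Y2 and DB = B1 − B2.

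- Var(DY) = Var(DB) = 2s²(1 − rb), and Cov(DY, DB) = 2s²(rw − rb).
- Their correlation is k = (rw − rb)/(1 − rb).
- No baseline: 2s²(1 − rb).
- Change scores: Var(DY − DB) = 4s²(1 − rw) = 4s²(1 − rb)(1 − k).
- Covariate-adjusted: 2s²(1 − rb)(1 − k²).
- Change ÷ adjusted = 2(1 − k)/(1 − k²) = 2/(1 + k), which is at least 1 for every k.
- Change ÷ no baseline = 2(1 − k), which is below 1 only when k > 0.5, that is, when rw > (1 + rb)/2.

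**Results.** The number of patients to which 60 are equivalent is 60(1 + k)/2.

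| rb, rw (assumed) | k | Variance, change ÷ adjusted | SE larger by | 60 patients act like | Variance, change ÷ no baseline |
|---|---|---|---|---|---|
| equal | 0 | 2.00 | 41% | 30 | 2.00 |
| 0.5, 0.6 | 0.2 | 1.67 | 29% | 36 | 1.60 |
| 0.8, 0.9 | 0.5 | 1.33 | 15% | 45 | 1.00 |
| share 0.75 | 0.75 | 1.14 | 7% | 52.5 | 0.50 |

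In the last row, a patient-by-period component makes up 75% of the within-patient variance. A simulation of the equal-correlation case with 400,000 patients gave a change ÷ no-baseline ratio of 2.01.

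**Serial correlation on the actual visit days.** Day 14 is 14 days from its own baseline and 15 days from the Day 29 baseline, so it is scarcely closer to its own. With a stable patient effect plus first-order autocorrelation, 14-day correlations from 0.1 to 0.97 give k from 0.06 to 0.50. The change ÷ adjusted ratio then runs from 2/1.06 = 1.89 to 2/1.50 = 1.33 (SE 37% to 15% larger). Adding independent day-to-day noise gives k from 0.03 to 0.18, and ratios from 2/1.03 = 1.94 to 2/1.18 = 1.69.

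**On an absolute scale.** Assume a log-scale within-patient SD of 0.3 per recording, N = 60 and k = 0. The 95% half-width is 1.96 × 0.3 × √(2/60) = 0.107 adjusted, against 1.96 × 0.3 × √(4/60) = 0.152 with change scores. For assumed SDs of 0.2 to 0.5 the ranges are 0.072 to 0.179 and 0.101 to 0.253.

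**Other readings of baseline.** A single common baseline cancels, so nothing is added relative to using no baseline (ratio 1.00). If Period 1 averaged the screening and pre-dose recordings, the equal-correlation ratio to no baseline would be (2 + 0.5 + 1)/2 = 1.75.

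**The case against.** The strongest reply is that the documents never state the analysis being criticised. Table 1 says only that change is measured from baseline, and the period-specific baseline is inferred from the recording schedule and the summary of changes. That stands, and it is why the fix must define baseline. The inference is still a good one, since the summary of changes calls the Day 29 recording a baseline for Period 2.

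A second reply is that a change endpoint does not by itself lose precision: regressing DY − DB on DB gives the same treatment estimate and standard error as regressing DY on DB. That also stands, so Table 1 need not be rewritten. The loss comes from leaving the adjustment out.

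Third, no test or power target is set, so no stated operating characteristic is missed. For patients with only one period, a change score can remove between-patient variation. Both points are correct. They limit the matter to precision and are a reason to keep change from baseline as a descriptive summary.

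A reader might go further and infer three things that the documents do not support:

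- **That subtraction always adds noise.** It does so relative to using no baseline only when k is below 0.5, and no correlations are reported.
- **That doubling is the expected size.** It is the figure for equal correlation, and the largest in the structures tried.
- **That drug effect remaining at Day 29 biases the change score.** Table 4 puts five half-lives at about 4 days, or 0.8 day each. Day 14 to Day 29 is 15 days, roughly 19 half-lives, so the documents offer no basis for a carryover figure.

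**Conclusion.** The concern holds as a conditional loss of precision. If each period's pre-dose recording is the baseline and change scores are contrasted without adjustment, the variance is 2/(1 + k) times what the same data allow. The standard error is 41% larger at k = 0, and 29% to 15% larger for assumed k of 0.2 to 0.5.

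These sizes rest on equal variances across recordings and on assumed correlations. The ordering needs neither: subtraction fixes the baseline slope at 1 and adjustment estimates it, so adjustment loses at most about one degree of freedom. The algebra is the same on the absolute or the log scale. The point is worth acting on because the gain costs nothing in data, but it does not invalidate the design or the endpoint.

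**What to change.** In Section 6.4, state that:

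- baseline is the pre-dose 24-hour recording of each treatment period, and on which scale cough frequency is analysed;
- GDC-6599 minus placebo is estimated from the within-patient difference, allowing for period, with the within-patient difference in period baselines as a covariate. One form regresses Y1 − Y2 on treatment sequence and B1 − B2, and half the sequence coefficient is the treatment effect;
- an equivalent crossover mixed model with a period effect may be used instead, provided that the patient-mean baseline and the period's deviation from it enter as separate covariates.

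The response may be Day 14/Day 43 cough frequency or change from baseline, since both give the same adjusted estimate. Table 1 can keep its wording, and change from baseline can stay as a descriptive column. The cost is a few sentences of statistical text and one degree of freedom, with no extra recordings, visits or patients.
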